* Messages emphasize the benefits of being vaccinated; ** Messages emphasize the risks of not getting vaccinated.

Subject Population

There are approximately n = 430,000 patients in the primary care registry (RCT#2) who are active/inactive portal users and affiliated with the primary care practices of interest for this research. And additional 50,000 meet the SUPREME criteria for diabetes.

Many patients are members of the same family. As such, the research team will assemble family units (using household address, primary telephone number, patient ID of the guarantor, and insurance member ID as the variables of commonality to create these family units). For RCT 2, for each family, 1 individual will be randomly selected as the index patient for each age or diabetic subgroup. Only index patients who are also active portal users and affiliated with a primary care practice (criteria explained below) will have their data analyzed as part of the primary analysis plan.

Secondary analyses will involve all study subjects.

Gender and age: We anticipate the gender distribution to be roughly equal. All ages of patients will be included in the study; however, patient will not receive a message until they are 6 months of age, as the flu vaccine is not recommended for those less than 6 months of age.

Racial and ethnic origin: There are no enrollment restrictions based on race/ethnicity.

Inclusion criteria

A patient at one of the clinics of interest within the UCLA Health System (up to 55 practices). An individual is deemed a primary care patient of the UCLA Health System through the following algorithm:

Assigned managed care patients (UCLAMG) + Attributed patients from other payers/ACOs

≥2 PCP visits in the past 3 years; or

≥1 PCP visit with preventive service code in past 1 year (99381-99397 or G0438/G0439)

All visits cannot be urgent care visits (i.e., excludes visits after hours or on weekends, not by urgent care codes since UCLA does not bill accordingly)

Active patient: We decided to use the algorithm outlined above and currently approved and in place by the UCLA Health System as the research team believes it to be a generalizable model that could be applied to other health systems.

Creating family units

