3. The patient was randomly selected as the index patient in their family unit for one of the age group/diabetic groups

We will assess primary intervention effects among eligible index patients, and secondary analyses for the entire primary care registry since the impact of the intervention reflects the extent of portal penetration and high correlation that exists among members of the same family (up to 480,000 patients for RCT #2, (ISS-generated data extraction: of 430,000; IP-generated data extraction of approximately 50,000 patients meeting the SUPREME criteria for diabetes (MRNS only shared with the study team by the IP group).

Exclusion criteria

Patients will be excluded from the overall study if they are not part of UCLA's primary care registry per the above algorithm detailed in the inclusion criteria.

MEASURES

Dependent Measures

Vaccine Outcome: The primary outcome is influenza vaccination during the vaccination season as measured by analysis of EHR data. For children <9y who had not received prior influenza vaccination, the outcome will be at least 1 influenza vaccination.

Process Outcomes: These will include: (a) total # visits to the practice during the study time period, (b) # flu vaccine or nurse visits, and (c) missed opportunities. Visits will be measured by the EHR, using ICD-10/CPT codes to classify visits to primary care as preventive, acute/chronic, or nurse-vaccination. Missed opportunities are defined as # vaccine-eligible visits during which the patient did not receive an influenza vaccination. These

process metrics will help assess how the intervention worked.

Cost and Cost Effectiveness

Costs: Since the intervention is implemented centrally, we assume no added practice costs. We also assume practice costs/vaccination from portal R/R is identical to standard practice costs/vaccination. We will assess the time and costs of study and implementation personnel and non-personnel costs, distinguishing planning costs from intervention costs. We will measure costs using a standardized time study/resource survey sent weekly to all individuals working on the study that delineates (a) the # hours spent for each individual, and (b) research vs implementation time. We will use national salary estimates by work code from the Bureau of Labor Statistics to value personnel time in standard rates. We will measure non-personnel costs EHR hardware, software, materials.

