We will employ intent-to-treat analyses using mixed effects log-binomial regression models with practice random effects, an approach recommended for RCTs in which the goal is to estimate the causal effects of interventions on individuals, adjusted for clustering of patients by practice. The primary model terms will be reminder arm (gain-frame v. loss-frame v. none), and pre-commitment arm (prompt v. no prompt). Models will adjust for the following patient characteristics: age, gender, race/ethnicity, primary language, primary payor, and prior receipt of influenza vaccines in the last two years. Evaluation of study hypotheses will be performed using model contrasts, and treatment effects will be reported in terms of risk ratios and 95% CIs. In the event of computational issues, we will replace the log-binomial specification with a log-Poisson specification, and use model-robust standard errors for inference on treatment effect risk ratios.

Additional Analysis

Additional analyses will include evaluation of process measures (e.g., missed opportunities), evaluation of effect modification by patient characteristics, comparison of the gain-frame and loss-frame arms, and evaluation of vaccination receipt including self-reported vaccinations. Process measures will be analyzed similarly to the primary outcome but using different distributions and link functions as appropriate (e.g., negative binomial distributions for number of missed opportunities). Effect heterogeneity will be evaluated by introducing interaction terms into the primary model specification. All secondary analyses will use a significance level of 0.05. All analyses will be performed using SAS v. 9.4 (SAS Institute Inc., Cary, NC).

Process measures: We assessed the percentage of patients who opened the portal reminder letter, as well as the source of influenza vaccination data (health system within UCLA practices, external source via data transfer, patient/proxy update through normal portal processes, or patient/proxy update in response to portal reminders).

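### Visit-based process outcomes are to be modelled without the patient's pre-randomisation visit count, which gives up some precision on secondary results

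*Combined protocol and SAP*

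**What the plan says.** The Primary Analysis section specifies "mixed effects log-binomial regression models with practice random effects" and lists the adjusting characteristics: "age, gender, race/ethnicity, primary language, primary payor, and prior receipt of influenza vaccines in the last two years". No measure of earlier visit frequency is among them.

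The Process Outcomes paragraph under Measures opens its list with "a) total # visits to the practice during the study time period". It then adds flu vaccine or nurse visits, and missed opportunities, which are counted from vaccine-eligible visits. It says these measures help to show how the intervention worked.

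The Additional Analysis section states: "Process measures will be analyzed similarly to the primary outcome but using different distributions and link functions as appropriate". Its example is a negative binomial distribution for missed opportunities. It names no further covariate.

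The Inclusion criteria use "PCP visits in the past 3 years" as part of the algorithm that defines a primary care patient, so visit history before the study is in the EHR and is already queried.

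**The concern.** The covariate list fits the vaccination outcome: it contains that outcome's own history. Carried over to visit counts, it lacks the corresponding item. Past use of a practice is a natural predictor of later use, and for total visits it is the baseline value of the same measure. For nurse or vaccine visits and missed opportunities it is a close relative, because both arise from visits.

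A portal letter may shift visit counts only slightly. If the confidence intervals for these outcomes are wider than they need be, the trial can say less about whether reminders or prompts acted through extra visits or through fewer missed opportunities.

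**Working it through.** **Inputs.** The covariate list, the process outcomes and the carry-over rule are as cited above. The documents state no visit rate, no correlation between earlier and later visits, no sample size and no number per arm. There is thus no figure of the plan's to reproduce, and everything below rests on assumed values.

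**Step 1: size for visit outcomes.** With r the correlation between the baseline count and the study-period count, adjustment multiplies the variance of the arm effect by about 1 − r². The SE is multiplied by √(1 − r²), and the equivalent gain in patients is 1/(1 − r²) − 1.

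| Assumed r | Variance factor | SE factor | SE reduction | Equivalent extra patients |
|---|---|---|---|---|
| 0.2 | 0.96 | 0.980 | 2% | 4% |
| 0.3 | 0.91 | 0.954 | 5% | 10% |
| 0.4 | 0.84 | 0.917 | 8% | 19% |
| 0.5 | 0.75 | 0.866 | 13% | 33% |
| 0.6 | 0.64 | 0.800 | 20% | 56% |

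**Step 2: check by simulation.** The set-up was 400,000 patients, three equal reminder arms crossed with two prompt arms, no practice clustering, and a log-Poisson model with robust SE. With r between baseline and study-period visits of about 0.42, adding log(1 + baseline visits) multiplied the SE by 0.914 to 0.916, a cut of 8 to 9%. The formula gives √(1 − 0.42²) = 0.908, so the two agree closely.

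**Step 3: allowance for covariates already planned.** The r that matters is the partial correlation, given age, gender, payor and the rest, within a cohort. Neither calculation above includes age, gender or payor. If they lowered r from 0.4 to 0.3, the SE reduction would fall from 8% to 5%.

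**Step 4: does the same argument reach the primary outcome?** In the same simulation, with vaccination at about 50% and a correlation of 0.04 to 0.14 between baseline visits and vaccination, adding visits to a model with any-versus-none prior vaccination multiplied the SE of the log risk ratio by 0.9901 to 0.9991. That is a gain of 0.1 to 1.0%.

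**Step 5: coding of prior vaccination.** The plan's words are "prior receipt of influenza vaccines in the last two years". An any-versus-none term, a count of 0, 1 or 2, and one term per season all fit them. Compared with any-versus-none, season terms with their interaction multiplied the simulated SE by 0.9545 to 0.9787, a cut of about 2 to 4.5%. Compared with the count, the cut was about 1.2 to 1.5% (for example 0.9787/0.9913 = 0.987). If season terms are already meant, it is nil or close to nil. In absolute terms, at an assumed 10,000 per arm, 50% uptake, two-sided 0.05 and 80% power, the detectable difference is 1.98 points. The largest of these gains would take it to 1.98 × 0.9545 = 1.89.

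**The case against.** The case for leaving the plan alone has several parts.

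- **Importance.** Visits are additional analyses and none of the stated hypotheses concerns them. Omitting a baseline covariate in a randomised comparison neither biases the estimate nor inflates type I error. This stands, and it limits the point to efficiency on secondary outcomes.
- **Size.** Every r is assumed, and the planned covariates and cohort stratification take up part of the gain. This also stands. It shrinks the benefit but gives no reason to expect it to vanish.
- **Wording.** Analysing process measures similarly does not expressly forbid another covariate. True, but the sentence names what will differ, and covariates are not among the differences.
- **Convergence.** The plan foresees computational trouble, and extra predictors can add to it. That worry attaches to the log-binomial vaccination model, not to count models for visits.
- **Data.** The registry algorithm also takes in assigned and attributed patients, the waiver request limits health information to the minimum necessary, and infants lack a full year of history. These are practical matters for the query. The look-back draws on the same kind of EHR visit data as the outcome, and age is already in the model.

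A reader might go further and infer that prior vaccination is entered as a single any-versus-none term, so that the primary contrasts lose precision. The documents do not support this, because no coding is given. Nor do they support the inference that the vaccination model needs a visit count: the illustrated gain there is 1% or less.

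**Conclusion.** The point holds for the visit-based process outcomes only. As written, their models omit a relevant baseline measure whose source data are already in use. The cost is about 2% in SE if r is 0.2, 8% if it is 0.4 and 13% if it is 0.5, and somewhat less after the planned adjustment. These figures depend on assumed correlations. Because numbers per arm and cohort are not stated, the effect on absolute interval widths cannot be given. There is no bias and no threat to the primary conclusions. The improvement is modest, and worth making because it is cheap. The unspecified coding of prior vaccination is a gap in detail, not a demonstrated error.

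**What to change.** Add one sentence to Additional Analysis: the models for total visits, flu vaccine or nurse visits, and missed opportunities will also include the patient's PCP visit count over a fixed look-back ending before randomisation, for example log(1 + count) over 12 months. State how infants with less than 12 months of history are handled, for example by counting over the time available, with age in the model as planned.

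The cost is SAP wording and one further EHR query on earlier dates, after a check that the look-back is covered by the data request in the waiver. No new data collection from patients is needed.

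Leave the primary vaccination model's covariates as they are. As a minor clarification, state how prior vaccination is coded, for example one indicator per season, with a rule for children too young to have had two seasons. Settle both points before outcome data are seen.

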Aim 2 RCT #2: In addition, we will test the impact of a "pre-commitment" question asking whether the patient plans to receive the flu vaccine (prior to the reminders going out). This question will be asked of half of patients per arm of the 3-arm RCT. Previous research has indicated pre-commitment can improve the likelihood a patient follows through with a behavior. We intend to determine whether pre-commitment increases the likelihood of getting the flu vaccine.

In summary, families will be randomized using a 3x2 factorial allocation (no reminder v. positively-framed reminder v. negatively-framed reminder, and no pre-commitment question v. pre-commitment question). Family members will be divided into 4 non-overlapping cohorts (age <18 years, 18-64 years non-diabetic, 65+ years non-diabetic, and 18+ years diabetic), and a single index member per family per cohort will be selected for inclusion in the study. Only active users affiliated with a UCLA primary care practice will be included in the study sample. For single individuals not part of a family, that individual will serve as the index patient.

Hypotheses:

Hyp 1 RCT #2: Vaccination rates will differ by receipt of no reminders, positively framed reminders and negatively framed reminders.

1.1 Vaccination rates will be higher among patients receiving positively framed reminders than among patients receiving no reminders.

1.2 Vaccination rates will be higher among patients receiving negatively framed reminders than among patients

receiving no reminders.

1.3. Vaccination rates will be higher among patients receiving positively framed reminders than among patients receiving negatively framed reminders.

Hyp 2 RCT #2: Vaccination rates will be higher among patients receiving a pre-commitment question than among patients not receiving the pre-commitment question.

2.1 The arm receiving the pre-commitment question, asking about their intention to get the flu vaccine (prior to the reminders going out), are more likely to follow through with influenza vaccination; therefore, the pre-commitment arm will have higher rates of flu vaccination than the control arm for the pre-commitment component.

The RCT design, subpopulations and letter components have been approved by the MyChart subcommittee, Ambulatory Operations Advisory Group, and the UCLA Health Primary Care Committee.

METHODS AND STUDY PROCEDURES

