The study does not represent more than minimal risk. The objective is to encourage patients to schedule a visit to see their primary health care provider and to make an appointment to receive a recommended vaccine. The vaccine is recommended by the Advisory Committee of Immunization Practices (ACIP) for all individuals over the age of 6 months and older on an annual basis. Therefore, indicating a patient is due for an influenza vaccination does not represent sensitive information. In addition, the message will only be delivered and accessible via the patient portal which is username and password protected. The greatest risk is one of loss of confidentiality.

BENEFITS TO SUBJECTS

The benefit to the subject is reminders to receive a recommended vaccine that offers protection from influenza, which can be very serious and can require hospitalization or can lead to death in some cases.

The benefit to society would be a better understanding of effective R/R messages and modalities that could be scaled up nationally and disseminated to other health systems to increase influenza vaccination (improve individual and herd immunity). This is particularly important for the influenza vaccine as in today's current society many have decided to forgo essential and recommended vaccines for themselves and their children, thereby increasing their personal risk.

COSTS FOR PARTICIPATION

Subjects will not incur any financial obligations from participation in the study.

PAYMENT FOR PARTICIPATION

No payments will be received by subjects.

STATISTICS AND ANALYTIC PLAN

Primary Analysis

We hypothesize that patients receiving gain-framed or loss-framed portal R/R messages will have higher influenza vaccination rates than no R/R, and we hypothesize that patients receiving pre-commitment prompts will have higher influenza vaccination rates than no prompts. Primary outcomes (patient receipt of flu vaccine) are binary; our main explanatory variable will be an indicator for the receipt of any portal-based R/R or prompt.

The analysis will be based on a 3x2 factorial design, with evaluation of a reminder framing intervention (gain-frame v. loss-frame v. no reminder), and a pre-commitment prompt intervention (pre-commitment v. no pre-commitment). Analyses will be stratified into 4 patient cohorts: <18y, 18-64 non-diabetic, 65+ non-diabetic, and 18+ diabetic. The pediatric age group (<18y) will be analyzed separately.

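### Secondary analyses that include whole families need family-clustered standard errors; the stated model accounts only for practice

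*Combined protocol and SAP*

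**What the plan says.** **Randomisation and analysis sets.** The allocation summary in Specific Aims makes the family the unit of the 3x2 randomisation and takes one index member from each family in each of four cohorts. Subject Population, and the section on selecting the index patient for primary analysis, limit the primary analysis to index patients who are active portal users affiliated with a practice. The same two places put secondary analyses on all subjects in the primary care registry, up to 480,000. The second gives high correlation within families as part of the reason.

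**Model.** Primary Analysis specifies "mixed effects log-binomial regression models with practice random effects", adjusted for patient characteristics that include recent influenza vaccination. It adds that "Evaluation of study hypotheses will be performed using model contrasts". If the model fails to compute, the fallback is a log-Poisson model with model-robust standard errors; no cluster unit is named.

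**Reuse.** Under Additional Analysis, "Process measures will be analyzed similarly to the primary outcome" with other distributions and links, and effect heterogeneity is examined by "introducing interaction terms into the primary model specification". The same paragraph states: "All secondary analyses will use a significance level of 0.05".

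**Framing.** Hypothesis 1.3 reads: "Vaccination rates will be higher among patients receiving positively framed reminders than among patients receiving negatively framed reminders". The opening of Primary Analysis restates only the comparisons with no reminder ("We hypothesize that patients receiving gain-framed or loss-framed portal R/R messages will have higher influenza vaccination rates than no R/R") and the prompt hypothesis. The "comparison of the gain-frame and loss-frame arms" then appears under Additional Analysis.

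**The concern.** When families are randomised, relatives get the same arm. Any correlation between their outcomes that the model leaves unexplained adds directly to the variance of the arm contrast. A practice random effect removes variation between practices; it does not capture the extra likeness of two people in one household. An analysis of the registry that follows the written specification would therefore treat relatives as independent given practice and covariates.

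At stake are the secondary results on process measures, on effect modification and on vaccination across the registry. Their confidence intervals would be too narrow and their tests would reject too often. The registry results describe population-level impact, which the protocol wants for dissemination to other health systems, so their stated precision matters.

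A smaller matter is the status of hypothesis 1.3. It is a numbered study hypothesis, but the restated primary hypotheses omit it and it reappears as an additional analysis. No sentence says which result decides it.

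**Working it through.** **Is there a plan figure to reproduce?** The documents give no sample size calculation, effect size, family size or intra-family correlation. The one sum available, 430,000 + 50,000 = 480,000, agrees with the stated registry size.

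**Inputs.** From the documents: family as the randomised unit, one index patient per family in each cohort for the primary set, the whole registry for secondary analyses, practice as the only random effect, and a 0.05 level (sidedness is not stated; two-sided is assumed here). Assumed: a share q = 0.2 to 0.5 of families have two members in a cohort and the rest have one; the within-family correlation r, after covariates and practice, is 0.1 to 0.5.

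**Formulas.**
- Size-weighted mean family size: mw = (1 + 3q)/(1 + q)
- Design effect: DE = 1 + (mw - 1)r
- True two-sided error at nominal 5%: 2 × (1 - Φ(1.96/√DE))
- Reported standard error as a fraction of the correct one: 1/√DE

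**Primary set.** With one patient per family, mw = 1, so DE = 1 and the error is 0.050. Within a cohort, no family term is needed.

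**Whole families.** q = 0.2 gives mw = 1.6/1.2 = 1.333; q = 0.5 gives mw = 2.5/1.5 = 1.667.

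| r | DE (q = 0.2 to 0.5) | True error |
|---|---|---|
| 0.1 | 1.033 to 1.067 | 5.4% to 5.8% |
| 0.3 | 1.10 to 1.20 | 6.2% to 7.4% |
| 0.5 | 1.167 to 1.333 | 7.0% to 9.0% |

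The standard error ratio runs from 1/√1.033 = 0.984 to 1/√1.333 = 0.866, so reported standard errors are about 2% to 13% too small.

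**Check of the formula.** Family-randomised binary data were simulated under the null with equal family sizes and analysed with independence standard errors on the log risk ratio (3,000 runs per setting).

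| Family size | r | Formula | Simulation |
|---|---|---|---|
| 1 | 0.3, 0.5 | 0.050, 0.050 | 0.045, 0.048 |
| 2 | 0.3, 0.5 | 0.086, 0.110 | 0.085, 0.111 |
| 3 | 0.3, 0.5 | 0.121, 0.166 | 0.121, 0.171 |

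The rows for sizes 2 and 3 confirm the formula; they are not estimates for this registry.

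**Pooling.** The plan stratifies into four cohorts but then says that the pediatric group is analysed separately, which leaves open whether the three adult cohorts might be combined. If they were, one family could supply up to three adult index patients, and the same correction would be needed even without the rest of the registry.

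**The case against.** The strongest reply is that the practice-only model stands under Primary Analysis, where it is adequate, and that no registry model is written at all. Nor does Additional Analysis say that process measures or effect modification will be run on the registry; the share who opened the letter can apply only to patients who were sent one. On this view the gap is silence, not a wrong specification. This stands in part: the inflation is conditional on the specification being reused unchanged on whole families. But secondary analyses are assigned to all subjects elsewhere in the protocol, and the only modelling instruction for them is to follow the primary model. The robust fallback does not close the gap, because it names no cluster unit.

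It can also be said that the inflation may be slight. Adjustment for prior vaccination would lower the residual correlation, and the low end of the range is 5.4%. That is fair. A further textual point is that Methods and Overall Study Design speak of randomising patients or participants; the explicit statement in Specific Aims, that families are randomised, is the one relied on here.

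A reader might infer that gain versus loss will be tested on the registry, so that hypothesis 1.3 has two competing tests, one diluted by patients who never log in. The documents do not establish this. No sentence places the framing comparison in the registry; that step requires equating additional with secondary analyses. The primary model has a three-level reminder term, so a contrast of two levels in index patients is the natural reading. What remains is an unclear label.

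**Conclusion.** The concern holds, conditionally. For any analysis in which a family contributes more than one patient, the written specification ignores a correlation that the protocol itself calls high, and both the 0.05 level and the 95% intervals would be too optimistic. Under the assumed inputs, the true error is about 5.4% to 9.0%; larger families or stronger correlation would raise it.

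A reader might infer that the trial's main results are compromised. They are not: the primary reminder and prompt comparisons, made within a cohort on index patients, need no family term. The status of hypothesis 1.3 is a minor point of clarity.

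**What to change.** Add to Additional Analysis: *Every analysis in which a family can contribute more than one patient, whether registry-wide or pooled across cohorts, will use robust standard errors clustered by family.* A workable form for vaccination receipt is the log-Poisson model already named as the fallback, with family as the cluster and practice as a fixed effect. This is preferable to adding a family random effect to the log-binomial model: families are built from address, telephone, guarantor and insurance identifiers, so relatives may attend different practices. The two groupings would then be crossed, in a model for which the plan already foresees computational trouble.

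As a minor clarification, add: *Hypothesis 1.3 (gain versus loss) is tested as a contrast of the primary model in active index patients; any registry-wide framing estimate is supplementary.*

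Family units are already constructed, so no new data are needed. The costs are slightly wider intervals in the affected analyses, practice indicators for up to 55 practices, and a framing result that describes active portal users. The registry-wide analyses otherwise stay as planned.
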